## 4 Sample Size

The target sample size is set to achieve a power of 90% for the comparison of the 1% OPA-15406 group and the vehicle group, which is firstly conducted in a closed testing procedure. In the phase 2 trial in pediatric patients in Japan (Trial 271-102-00002), the success rate in IGA was 37.5% (9/24), 40.0% (10/25), and 8.3% (2/24) in the 0.3% OPA-15406 group, the 1% OPA-15406 group, and the vehicle group, respectively. However, for reasons such as the sample size of the phase 2 trial in pediatric patients in Japan being small and in order to conservatively consider the robustness of the trial results based on the characteristics of the primary endpoint, it is assumed that if the number of responders decreased by one and increased by one in the 1% OPA-15406 group and vehicle group, respectively, then the success rate in IGA is 36% and 12%. In the case of this condition, it is necessary to have 72 subjects per group to achieve a power of 90% at a two-sided significance level of 5%. In consideration of an exploratory assessment of age categories, however, the target sample size has been set as 80 subjects in each group, for a total of 240 subjects.

## **5 Statistical Analysis Datasets**

### **5.1 Full Analysis Set (FAS)**

The FAS consists of all subjects who have received the IMP at least once.

### **5.2 Safety Set (SS)**

The SS consists of all subjects who have received the IMP at least once.

### **5.3 Handling of Missing Data**

For the success rate in IGA, the primary endpoint, subjects with missing IGA data will be handled as non-responders. Subjects with only baseline values or with data missing at any timepoint will also be handled as non-responders.

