3.5 Endpoints

3.5.1 Primary Endpoint

Success rate in IGA at Week 4: percentage of subjects with IGA score of 0 or 1 with improvement by at least 2 grades. Subjects with missing IGA data will be handled as non-responders.

[Rationale for Primary Endpoint]

Investigator's Global Assessment evaluates the systemic clinical characteristics (erythema, infiltration, papulation, oozing, and crusting) by the severity score of IGA (0 = Clear, 1 = Almost clear, 2 = Mild disease, 3 = Moderate disease, 4 = Severe disease/Very severe disease) and clearly distinguishes each score. In patients with AD, as remission or close to remission is the goal of the treatment¹, clinical characteristics of remission or close to remission are defined as IGA score of 0 (Clear) or 1 (Almost clear), and clinically significant improvement as improvement in IGA by at least 2 grades.

Based on the above, the success rate in IGA (percentage of subjects with IGA score of 0 or 1 with improvement by at least 2 grades) at Week 4 is established as the primary efficacy endpoint.

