7.3 Handling of Missing Data

For the success rate in IGA, the primary endpoint, subjects with missing IGA data will be handled as non-responders.

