### **3.4 Trial Visit Window**

The start date of IMP administration is defined as baseline (Day 1) to count the number of days after starting IMP administration. Unscheduled visit data and withdrawal visit data as well as scheduled visit data will be included to determine timepoints for analysis. For efficacy endpoints, data up to 3 days after the end of IMP administration (final day of IMP administration + 3 days) will be included in the analysis. For safety endpoints, all data from the first IMP administration will be included in the analysis. Timepoints for analysis and acceptable windows are shown in Table 3.4-1. If there are multiple data points within an acceptable window, the last one in the window will be used. The Last Visit data for efficacy endpoints will be from the last visit during the period from the day after the first day of IMP administration (Day 2) through the third day after the last IMP administration (including unscheduled and withdrawal visit data), and those for safety endpoints will be from the last visit available from all data after the first day of IMP administration.

The baseline data for analysis will be from the visit closest and prior to the first day of IMP administration.

For the Verbal Rating Scale (VRS), the patient diary will be used as the source of data for the period from the start date of IMP administration (Day 1) through Day 8. After Week 1, CRF Visit data (including unscheduled and withdrawal visit data) excluding patient diary data will be used to specify the timepoints for analysis according to Table 3.4-1. If there are multiple data points within an acceptable window, the last one in the window will be used.

Table 3.4-1 Trial Day and Visit Windows				
Timepoint	Target Day	Interval (days after starting administration)		
Baseline	1	—	to	1
1 day after start of IMP administration (VRS alone)	2	—	to	—
2 days after start of IMP administration (VRS alone)	3	—	to	—
3 days after start of IMP administration (VRS alone)	4	—	to	—
4 days after start of IMP administration (VRS alone)	5	—	to	—
5 days after start of IMP administration (VRS alone)	6	—	to	—
6 days after start of IMP administration (VRS alone)	7	—	to	—
7 days after start of IMP administration (VRS alone)	8	—	to	—
8 days after start of IMP administration (VRS alone)	9	—	to	—
Week 1	8	2	to	10
Week 2	15	11	to	21
Week 4	29	22	to	32

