## **6 Primary and Secondary Outcome Variables**

### **6.1 Primary Outcome Variable**

Success rate in IGA at Week 4: percentage of subjects with IGA score of 0 or 1 with improvement by at least 2 grades.

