### 8.1.1 Primary Efficacy Analysis

The efficacy of the 0.3% and 1% OPA-15406 groups will be demonstrated compared to the vehicle group based on the primary endpoint, the success rate in IGA at Week 4. Overall type I errors will be controlled using a closed testing procedure. First, the 1% OPA-15406 treatment group and the vehicle group will be compared. If significant at the two-sided significance level of 5%, the 0.3% OPA-15406 treatment group and the vehicle group will then be compared at the two-sided significance level of 5%. The Cochran-Mantel-Haenszel test will be conducted for comparison using the baseline IGA (2 or 3) and age (“2 to 6 years” or “7 to 14 years”) as a stratification factor. The difference in the success rate in IGA and its two-sided 95% confidence interval (common risk difference adjusted by Mantel Haenszel method and its two-sided 95% confidence interval) between the vehicle group and 0.3% or the 1% OPA-15406 group will be determined. Also, the two-sided 95% confidence interval of the success rate in IGA in each treatment group (based on Clopper-Pearson method) will be calculated. In addition, the success rate in IGA in each treatment group at Week 4 and its two-sided 95% confidence interval will be plotted and the dose-response relationship will be graphically assessed.

The SAS code for the Cochran-Mantel-Haenszel test and to determine the difference in the success rate and two-sided 95% confidence interval is as follows:

```
proc freq ;
  tables Agegroup*BaselineIGA*Treatment*Response / riskdiff(common) cmh ;
run;
```

A supplementary analysis will be performed using data which includes missing data imputed by Last Observation Carried Forward (LOCF) and Observed Cases (OC) data which does not include the imputed missing data in the same manner.

Data at Weeks 1 and 2 will also be analyzed in the same manner as the primary endpoint at Week 4.

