### 8.2 Secondary Efficacy Endpoints

#### 8.2.1 Success Rates in IGA (Revised Definition) and EASI

The success rate in achieving an IGA score of 0 or 1 (revised definition from primary efficacy endpoint) by Week 4 and the success rate in EASI 75, EASI 90, and EASI 50 by Week 4 will be analyzed in the same manner as the primary endpoint in [Section 8.1.1](#)

For IGA, subjects who achieve a score of 0 or 1 in IGA will be handled as responders and subjects who do not achieve a score 0 or 1 in IGA will be handled as non-responders. Subjects with missing IGA data will be handled as non-responders.

EASI 75 will be set as the important secondary endpoint, and subjects whose percentage change in their total EASI score from baseline decreases by  $\geq 75\%$  will be handled as responders and subjects whose percentage change from baseline does not decrease by  $\geq 75\%$  will be handled as non-responders. Subjects with missing EASI 75 data will be handled as non-responders. EASI 90 and EASI 50 will be analyzed in the same manner. Similarities with the primary endpoint results will be assessed using response rates in EASI (EASI 75, EASI 90, and EASI 50).

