## **14 Changes in the Planned Analyses**

The following calculations specified in [Section 7.6.2](#) in the protocol were not performed.

- The number and percentage of subjects who are in the potentially clinically significant range will be calculated.

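### SAP 5.3 as worded turns an observed Week 4 IGA success into a failure when the Week 1 or Week 2 IGA is missing (minor wording error on the primary responder flag)

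*SAP*

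**What the plan says.** SAP 6.1 defines the primary outcome as "Success rate in IGA at Week 4: percentage of subjects with IGA score of 0 or 1 with improvement by at least 2 grades". Only the baseline and Week 4 scores enter that definition. Protocol 3.5.1 adds one missing-data rule, "Subjects with missing IGA data will be handled as non-responders", and protocol 7.3 repeats it for the primary endpoint.

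SAP 5.3 restates the protocol rule in its first sentence. Its second sentence goes further: "Subjects with only baseline values or with data missing at any timepoint will also be handled as non-responders".

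Three other places bear on how to read it:

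- SAP 3.4 sets the analysis windows at Days 2–10 (Week 1), 11–21 (Week 2) and 22–32 (Week 4), and says "Unscheduled visit data and withdrawal visit data as well as scheduled visit data will be included to determine timepoints for analysis".
- SAP 8.1.1 says "Data at Weeks 1 and 2 will also be analyzed in the same manner as the primary endpoint at Week 4".
- SAP 8.2.1 says of the IGA 0/1 and EASI responder rates, ending with EASI 50, "EASI 50 by Week 4 will be analyzed in the same manner as the primary endpoint". It then restates only the simple missing-data rule for them.

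**The concern.** The added sentence classifies the subject, not the subject at a given visit, and the word *also* marks it as an addition to the rule before it. IGA is assessed after baseline at Weeks 1, 2 and 4. Read as written, a gap at Week 1 or Week 2 therefore overrides a success actually observed at Week 4.

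At stake is the derivation of the primary responder flag. Two competent programmers could build different flags from the same data, one from the SAP sentence and one from the protocol definition, and each could cite a governing text. The planned observed-cases and LOCF analyses would show whether many children were recoded. They would not show which flag was the planned primary one.

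It is also unclear whether the added sentence carries over to IGA 0/1 and EASI 50/75/90, since SAP 8.2.1 both borrows the primary method and restates the shorter rule.

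**Working it through.** **1. The rules side by side**

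| Child's IGA record | Protocol 3.5.1 and 7.3, SAP 6.1 | SAP 5.3, second sentence, literal |
|---|---|---|
| Week 4 missing | non-responder | non-responder |
| Baseline only | non-responder | non-responder |
| Weeks 1, 2 and 4 present, Week 4 success | responder | responder |
| Week 1 or Week 2 missing, Week 4 success | **responder** | **non-responder** |

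The rules differ only in the last row.

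**2. Inputs**

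- Planning rates: 36% (1% group) and 12% (vehicle); 80 per arm; two-sided 5% (protocol 7.1, SAP 4).
- q, the share of Week 4 responders with no Week 1 or no Week 2 IGA: not in the documents. It is an assumption, shown over a range; low values are the likelier ones.

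**3. The plan's own figure**

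For 90% power at 36% versus 12%, the plan states 72 per group. The pooled normal approximation gives 65 without continuity correction and 73 with it. Exact power of Fisher's test is 89.7% at 70, 90.2% at 71 and 90.7% at 72 per group. So 72 agrees closely with a conservative method, and the planning rates can be used as they stand.

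**4. Effect of the literal rule**

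Each success rate is multiplied by (1 − q). Power comes from exact enumeration of two independent binomials with n = 80 each. The test is the unstratified Mantel-Haenszel chi-square, with x successes on active, s successes in total and N = 160:

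χ² = (x − s/2)² / V, with V = n²·s·(N − s) / [N²(N − 1)]

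A result counts when χ² > 3.841 in favour of active.

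| q, equal in both arms | Rates | Difference (points) | Power |
|---|---|---|---|
| 0 | 36.0% vs 12.0% | 24.0 | 95.6% |
| 1% | 35.6% vs 11.9% | 23.8 | 95.4% |
| 2% | 35.3% vs 11.8% | 23.5 | 95.2% |
| 3% | 34.9% vs 11.6% | 23.3 | 94.9% |
| 5% | 34.2% vs 11.4% | 22.8 | 94.4% |
| 10% | 32.4% vs 10.8% | 21.6 | 92.8% |
| 15% | 30.6% vs 10.2% | 20.4 | 91.0% |

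Power reaches 90% at q of about 17%. Fisher's exact test is more conservative: 93.7% at q = 0, 93.1% at 2%, 92.1% at 5% and 90.0% at 10%.

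Expected responders per arm are 80 × 0.36 = 28.8 and 80 × 0.12 = 9.6. At q = 2%, the expected number recoded is 28.8 × 0.02 = 0.6 and 9.6 × 0.02 = 0.2.

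**5. Unequal q (hypothetical)**

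Nothing in the documents suggests that q differs by arm. If it did, the result could move either way:

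- 3% in the 1% arm only: 36 × 0.97 − 12 = 22.9 points, power 94.1%.
- 3% in the vehicle arm only: 36 − 12 × 0.97 = 24.4 points, power 96.2%.

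The planned stratified CMH test was not modelled, because the documents give no stratum-specific rates.

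**The case against.** The best defence is that the sentence means non-response at whichever timepoint is being analysed. SAP 8.1.1 applies the primary method to Weeks 1 and 2 as well, so a rule covering several timepoints is needed. SAP Appendix 3 lists figures of the IGA responder rate by visit. A subject-level penalty would distort those figures, since a child who responded at Week 1 and later dropped out would count as a Week 1 failure. The protocol is a translation, and the SAP code retains a Japanese label, so the English may be a loose rendering.

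Most of this stands as evidence of intent, and the per-timepoint reading is the more probable one. It does not rescue the text. Neither document states that reading, and under it the first sentence of SAP 5.3 already covers the case, so the second adds almost nothing.

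The objection is also right on two lesser points. SAP 14 declares one departure from the protocol, the dropped tabulation described as "The number and percentage of subjects who are in the potentially clinically significant range will be calculated". That the added rule is not listed there proves little, because the ANCOVA and the extra subgroups are not listed either. And SAP 8.2.1 does give its own missing-data rule, so a cross-reference there is a clarification, not a correction.

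The practical effect is limited as well. The windows are contiguous, and unscheduled visits can fill them. Ointment for the second two weeks is prescribed at the Week 2 visit (protocol 3.7.1.9), so few children would miss Week 2 and still have a usable Week 4 score.

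**Conclusion.** The point holds as a minor error. As worded, SAP 5.3 recodes an observed Week 4 success as a failure when an earlier IGA is missing, against the Week 4 endpoint in protocol 3.5.1 and SAP 6.1. The literal consequence follows from the text alone and needs no assumption.

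Its size rests on the assumed q. For plausible low values, fewer than one child per arm is expected to be recoded and power moves by about half a point. With q equal in both arms, power stays at or above 90% up to q of about 17% by the Mantel-Haenszel calculation, or about 10% by Fisher's test. The case for changing it is a single, unambiguous primary flag, not lost power.

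**What to change.** Replace the second sentence of SAP 5.3 with:

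> At each analysis timepoint (Week 1, 2 or 4), a subject whose IGA is missing at that timepoint, including a subject with baseline data only, is a non-responder at that timepoint. Missing data at another timepoint do not affect the Week 4 classification.

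In SAP 8.2.1, add a cross-reference applying the same rule, on the relevant score, to IGA 0/1 and EASI 50/75/90.

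Make the change before unblinding. If that point has passed, document which derivation was the planned one. The cost is one sentence and one cross-reference, with no change to data collection, visits or sample size.

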## **6 Primary and Secondary Outcome Variables**

### **6.1 Primary Outcome Variable**

Success rate in IGA at Week 4: percentage of subjects with IGA score of 0 or 1 with improvement by at least 2 grades.

### **6.2 Secondary Outcome Variables**

- Success rate in IGA at Week 4: percentage of subjects with improved IGA score of 0 or 1 (revised definition from primary outcome variable)
- Change from baseline at Week 4 in the IGA score
- Success rate in EASI 75 (improvement of  $\geq 75\%$  in EASI), EASI 90 (improvement of  $\geq 90\%$  in EASI), and EASI 50 (improvement of  $\geq 50\%$  in EASI) at Week 4
- Change from baseline at Week 4 in the total EASI score and each EASI clinical sign score
- Change from baseline at Week 4 in VRS for pruritus
- Change from baseline through Day 8 in VRS for pruritus
- Change from baseline at Week 4 in the total Patient-Oriented Eczema Measure (POEM) score
- Change from baseline at Week 4 in the total affected BSA (%)

## 7 Disposition and Demographic Analysis

### 7.1 Subject Disposition

The number of subjects screened and the number of subjects allocated will be calculated. Unless specified otherwise, the following tabulations will be presented by treatment group (0.3% OPA-15406, 1% OPA-15406, or vehicle). Frequency distribution (number and percentage, the same hereinafter) will be provided for subjects who received, who completed, and who discontinued IMP administration. Also, the number and percentage of subjects included in the statistical analysis datasets will be presented. The number of allocated subjects will be used as the denominator to calculate the percentage. For subjects who discontinued treatment, the frequency distribution by reason for discontinuation will be presented. Tabulations will also be presented by age categories (2 to 6 years old and 7 years and older).

### 7.2 Demographic and Baseline Characteristics

Based on the FAS and SS, age, sex, disease duration, body weight, height, body mass index (BMI), race, and severity of AD will be presented by treatment group and in total. The descriptive statistics will be presented for age, disease duration, body weight, height, and BMI; and frequency distribution for sex, race, and severity of AD. Medical histories and complications will be coded by System Organ Class (SOC) and Preferred Term (PT) using the Medical Dictionary for Regulatory Activities (MedDRA). Medical histories and complications will be listed but not summarized. Tabulations will also be presented by age categories (2 to 6 years old and 7 years and older).

For the computation of disease duration, date data that are partially missing will not be imputed. Where the month and day are missing, only the year will be used, and where the day is missing, the year and month will be used for calculation.

Where the “year, month, and day” are available:

$$(\text{Year-Month-Day} - \text{Year-Month-Day} + 1) / 365.25$$

Where only the “year and month” are available:

$$[(\text{Year} \times 12 + \text{Month}) - (\text{Year} \times 12 + \text{Month}) + 1] / 12$$

Where only the “year” is available: Year – Year + 1

### 7.3 Baseline Disease Evaluation

Based on the FAS and SS, the frequency distribution of baseline IGA scores (2 or 3) and the descriptive statistics for the total EASI (Eczema Area and Severity Index) score at baseline will be presented by treatment group and in total. The affected area will be

classified in the following categories, and the frequency distribution calculated by treatment group and in total. Tabulations will also be presented by age categories (2 to 6 years old and 7 years and older).

Affected area categories:  $\geq 5\%$  to  $< 10\%$ ,  $\geq 10\%$  to  $< 30\%$ , and  $\geq 30\%$

#### **7.4 Treatment Compliance**

Based on the SS, the compliance with the amount and number of doses from the baseline through Week 4 will be classified in the following categories, and the number and percentage of subjects will be calculated by treatment group and for all subjects. Also, the number and percentage of subjects administered will be calculated by week (Weeks 1, 2, 3, 4, 5, and Any Exposure). The method for calculating compliance will be defined in a separate analysis data set specification, etc.

Categories for compliance with the amount and number of doses:

$< 50\%$ ,  $\geq 50\%$  to  $< 60\%$ ,  $\geq 60\%$  to  $< 70\%$ ,  $\geq 70\%$  to  $< 80\%$ ,  $\geq 80\%$  to  $< 90\%$ ,  $\geq 90\%$  to  $< 100\%$ ,  $\geq 100\%$  to  $< 110\%$ ,  $\geq 110\%$  to  $< 120\%$ , and  $\geq 120\%$

Where the weight of IMP at retrieval is unknown, the amount of administration will be calculated by assuming that the retrieved weight is 0.

#### **7.5 Prior and Concomitant Medications**

Based on the SS, the number and percentage of subjects taking medications before the start of, during, and after the end of IMP administration will be calculated for each medication by treatment group and in total. Medications will be coded using WHO Drug Dictionary and summarized by ATC classifications level 2 and preferred name. Concomitant therapies will be listed but not summarized.

#### **7.6 Protocol Deviations**

Based on the allocated subjects, the number and percentage of subjects with major protocol deviations will be presented by treatment group and in total. Also for each site, the number and percentage of subjects with major protocol deviations will be presented by treatment group and in total.

### **8 Efficacy Analysis**

Based on the FAS, the following analysis will be performed.

#### **8.1 Primary Efficacy Endpoint**

The primary endpoint is the success rate in IGA at Week 4 (percentage of subjects with IGA score of 0 or 1 with improvement by at least 2 grades).

### 8.1.1 Primary Efficacy Analysis

The efficacy of the 0.3% and 1% OPA-15406 groups will be demonstrated compared to the vehicle group based on the primary endpoint, the success rate in IGA at Week 4. Overall type I errors will be controlled using a closed testing procedure. First, the 1% OPA-15406 treatment group and the vehicle group will be compared. If significant at the two-sided significance level of 5%, the 0.3% OPA-15406 treatment group and the vehicle group will then be compared at the two-sided significance level of 5%. The Cochran-Mantel-Haenszel test will be conducted for comparison using the baseline IGA (2 or 3) and age (“2 to 6 years” or “7 to 14 years”) as a stratification factor. The difference in the success rate in IGA and its two-sided 95% confidence interval (common risk difference adjusted by Mantel Haenszel method and its two-sided 95% confidence interval) between the vehicle group and 0.3% or the 1% OPA-15406 group will be determined. Also, the two-sided 95% confidence interval of the success rate in IGA in each treatment group (based on Clopper-Pearson method) will be calculated. In addition, the success rate in IGA in each treatment group at Week 4 and its two-sided 95% confidence interval will be plotted and the dose-response relationship will be graphically assessed.

The SAS code for the Cochran-Mantel-Haenszel test and to determine the difference in the success rate and two-sided 95% confidence interval is as follows:

```
proc freq ;
  tables Agegroup*BaselineIGA*Treatment*Response / riskdiff(common) cmh ;
run;
```

A supplementary analysis will be performed using data which includes missing data imputed by Last Observation Carried Forward (LOCF) and Observed Cases (OC) data which does not include the imputed missing data in the same manner.

Data at Weeks 1 and 2 will also be analyzed in the same manner as the primary endpoint at Week 4.

